1) Identify the rate at which blindly placed caudal blocks are not within the epidural space 2) Identify the rate at which ultrasound can guide a wrong block into the correct location 3) Identify if lack of heart rate change on incision can predict successful placement when medication administration is successfully confirmed with ultrasound 4) Identify if after using ultrasound to visualize placement, if concentrations of inhaled agents may be reduced in children

Section E: Protocol Risks/Subjects

E1. Risk Category

Category 1: Research not involving greater than minimum risk.

E2. Subjects

Gender:

Both

Age:

Child (3-12 yrs), Infant/Toddler (0-36 mos)

Ethnicity:

All Ethnicities

Primary Language:

English, Spanish

Groups to be recruited will include:

Patients

Which if any of the following vulnerable populations will be recruited as subjects?

Children

Vulnerable populations require special protections. How will you obtain informed consent, protect subject confidentiality, and prevent undue coercion?

Consent will only be obtained from parents/legal guardians. Confidentiality will be maintained by the PI as no patient or provider specific identifiers will be recorded aside from consent parental signature. To avoid undue coercion, consenting parents/guardians will be informed that their willingness to participate will not affect their child's treatment course or ability to get a caudal block or have any impact on their care course.

E3. Pregnant woman/fetus

Will pregnant women and/or fetuses (as described in 45 CFR 46 Subpart B) be enrolled in the research?

No

E4. Neonates

Will neonates of uncertain viability or nonviable neonates (as described in 45 CFR 46 Subpart B) be enrolled in the research?

No

E5. Children

Will children be enrolled in the research?

Yes

Section F: Design/Procedure

F1. Design

Select one category that most adequately describes your research:

c) Pilot

Discuss the research design including but not limited to such issues as: probability of group assignment, potential for subject to be randomized to placebo group, use of control subjects, etc.

Single blinded prospective trial in which all patients serve as their own clinical control group.

Inclusion Criteria:

Children ages 0-84 months Infra-umbilical procedure for which a caudal block is already planned American Society of Anesthesiology classifications of 1,2 or 3

Exclusion Criteria:

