Associated procedures for which caudal does not provide complete analgesia Incarcerated hernias Emergency procedures Local Anesthetic allergy Sacral dimple Rash over sacrum precluding block Parents/legal guardians unable to consent for surgical procedure in English language Foster Care/Child protective services as guardians Parental Refusal for caudal block or study participation American Society of Anesthesiology classifications other than 1,2 or 3

F2. Procedure

Patients meeting inclusion criteria and following informed consent will be brought back to the operating room. General anesthesia will be induced in the standard manner either by inhalation induction or intravenous induction at the discretion of the anesthesia attending of record. The airway will be secured using an

age/weight appropriately sized device, at the discretion of the anesthesia attending of record. The caudal block will ensue in the same manner regardless of the study at the discretion of the anesthesia attending of record. The attending anesthesiologist will perform or instruct the placement of a caudal block according to their standard of practice. At the time of administration of local anesthetic into the caudal space, the study collaborator (SC) will ultrasound the caudal space keeping the provider placing the block blinded to the imaging. The provider placing the block will inject 0.5mL of preservative free saline. The provider will then be asked to state if they are correctly in the caudal space or not. If the provider feels they are not in the caudal space, they will re-do the procedure. If the provider fails to identify incorrect location and this is noted by ultrasound, the SC will inform the provider to re-do the procedure. After a successful injection (as confirmed by ultrasound) is performed, the patient will be prepped for the procedure in standard manner. The inhaled anesthetic will be titrated until the minimal alveolar concentration is between 0.8-1 MAC for age prior to incision. The anesthesia provider will note the heart rate immediately before and after the first surgical stimulation. Data will be recorded de-identified on the sheet (see attached). The study PI will compare MAC hours (exposure to inhaled anesthetic agent) in patients having undergone caudal block with ultrasound confirmation to those in the retrospective group gathered for quality improvement to ascertain if reduction of exposure to inhaled agent was possible.

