Section G: Sample Size/Data Analysis

G1. Sample Size

How many subjects (or specimens, or charts) will be used in this study?

Local: 150 Worldwide: 150

Please indicate why you chose the sample size proposed:

A previous study using ultrasound in children for caudal block demonstrated an incidence of 7.1% subcutaneous bulging (failed block) when ultrasound was not used. Using our primary outcome of determination of block failure rate when performing blind (without ultrasound) and assuming a difference of 20% increase in success rate would alter practice and thus be clinically significant using a one sample mean, alpha of 0.05 and a power of 80% would require an enrollment of 99 patients, each serving as their own control. Assuming a study dropout rate of 10% (unknown sacral dimple, etc.) and requirement for additional patients to perform secondary statistical analyses, 150 patients will be enrolled. Analysis performed with JMP statistical software.

G2. Data Analysis

Provide a description of your plan for data analysis. State the types of comparisons you plan (e.g. comparison of means, comparison of proportions, regressions, analysis of variance). Which is the PRIMARY comparison/analysis? How will the analyses proposed relate to the primary purposes of your study?

Data will be presented as means +/-SD, median (range) and number % when appropriate. Continuous variables will be compared with independent sample t-test or Mann-Whitney U testing for normally distributed data. Odds ratios will be noted for the primary outcome with confidence intervals displayed to achieve CI of 95%. Statistics will be aided by JMP software with P values of <0.05 considered significant.

Section H: Potential Risks/Discomforts

Describe and assess any potential risks/discomforts; (physical, psychological, social, legal, or other) and assess the likelihood and seriousness of such risks:

There are no potential risk of discomfort to the patients As with all studies, there is a small risk of loss of confidentiality or data breach.

Section I: Potential Benefits

Describe potential benefit(s) to be gained by the individual subject as a result of participating in the planned work.

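### Objective 4 asks about inhaled agent concentration, but the only planned comparison is unadjusted MAC hours against a retrospective group, so case length or case mix could create or hide a reduction

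*Combined protocol and SAP*

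**What the plan says.** Objective 4, in Section D, is to find out, after ultrasound visualisation of placement, "if concentrations of inhaled agents may be reduced in children".

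The comparison that serves it is in F2: "The study PI will compare MAC hours (exposure to inhaled anesthetic agent) in patients having undergone caudal block with ultrasound confirmation". The comparator is a historical set of patients assembled earlier for quality-improvement work, and F2's stated aim is to learn whether exposure could be lowered. F2 also fixes a concentration range for the study patients: "The inhaled anesthetic will be titrated until the minimal alveolar concentration is between 0.8-1 MAC for age prior to incision". It refers to a data sheet ("Data will be recorded de-identified on the sheet (see attached") that is not part of the text available.

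For analysis, G2 states: "Continuous variables will be compared with independent sample t-test or Mann-Whitney U testing". It names no regression, matching, stratification or restriction. G1 gives no effect size, standard deviation or power for MAC hours. F1 describes patients as their own controls, but that cannot apply to a comparison with an outside group.

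**The concern.** Objective 4 concerns a concentration. MAC hours measure cumulative exposure, so they move with the length of the anesthetic as well as with its depth. The comparator is neither concurrent nor randomised, and nothing says it was selected by the study's eligibility criteria. Eligibility covers any infra-umbilical procedure with a planned caudal block at 0 to 84 months and ASA class 1 to 3, so there is room for operations of quite different length.

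A lower MAC-hours result could be read as showing that less agent was needed when it reflects shorter operations. An equal result could be read as no benefit when longer operations cancelled a real fall in concentration. Section I links lower exposure to possible neurodevelopmental benefit, so either misreading would matter.

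One source of extra time is not a bias. F2 provides that, if ultrasound shows an unrecognised misplacement, "the SC will inform the provider to re-do the procedure". Time added by that step, or by the ultrasound check itself, belongs to the effect of the strategy on exposure.

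**Working it through.** The plan states no figure for objective 4, so there is none to reproduce. The check has two parts.

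**1. Identity.** MAC hours = mean MAC × hours.

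- Equal concentration, shorter cases: 1.0 MAC × 1.0 h = 1.00 against 1.0 MAC × 0.8 h = 0.80. MAC hours fall 20% with no change in concentration.
- Lower concentration, longer cases: 1.0 MAC × 1.0 h = 1.00 against 0.8 MAC × 1.25 h = 1.00. A 20% cut in concentration disappears.

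**2. How often the unadjusted test would mislead.**

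Inputs:

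- Study n = 135: 150 enrolled less the dropout allowance in G1 ("Assuming a study dropout rate of 10" percent), 150 × 0.90 = 135.
- Two-sided alpha = 0.05: G2 gives the 0.05 threshold; two-sided is assumed.
- Retrospective m = 50, 100 or 150: assumption.
- Coefficient of variation (CV) of MAC hours = 0.4 to 0.6, and 1.0 as a wide case, the same in both groups: assumption.
- Ratio r of mean MAC hours, study to retrospective: assumption.

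Formulas, with the retrospective mean set to 1:

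- pooled variance = [(n − 1)(CV × r)² + (m − 1)CV²] / (n + m − 2)
- noncentrality = (r − 1) / [pooled SD × √(1/n + 1/m)]
- P(significant reduction) = lower-tail probability of the noncentral t beyond the 5% two-sided critical value

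One case in full, CV 0.5, m = 100, r = 0.90:

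- pooled variance = (134 × 0.2025 + 99 × 0.25)/233 = 0.2227, so pooled SD = 0.472
- standard error = 0.472 × √(1/135 + 1/100) = 0.0623
- noncentrality = −0.10/0.0623 = −1.61
- P = 35.9%

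Chance of a significant reduction **at equal concentration**, for m = 50 / 100 / 150 (nominal 2.5% in that direction):

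| CV | Cases 10% shorter (r = 0.90) | Cases 5% shorter (r = 0.95) |
|---|---|---|
| 0.4 | 36.7 / 51.6 / 59.5% | 11.9 / 16.1 / 18.8% |
| 0.5 | 25.3 / 35.9 / 42.1% | 9.1 / 11.8 / 13.6% |
| 0.6 | 18.9 / 26.5 / 31.1% | 7.5 / 9.5 / 10.7% |
| 1.0 | 9.5 / 12.3 / 14.0% | 5.0 / 5.8 / 6.3% |

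Chance of detecting a **true 10% cut in concentration**, for m = 50 / 100 / 150:

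| CV | Equal durations (r = 0.90) | Operations 5% longer (r = 0.90 × 1.05 = 0.945) | Operations 11.1% longer (r = 0.90 × 1.111 = 1.00) |
|---|---|---|---|
| 0.4 | 36.7 / 51.6 / 59.5% | 13.6 / 18.7 / 21.9% | 2.5% |
| 0.6 | 18.9 / 26.5 / 31.1% | 8.3 / 10.6 / 12.1% | 2.5% |
| 1.0 | 9.5 / 12.3 / 14.0% | 5.3 / 6.3 / 6.9% | 2.5% |

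The Mann-Whitney option does not avoid the problem. On simulated lognormal MAC hours (4,000 runs per cell, r = 0.90, equal concentration), it gave a significant reduction in 35.0% (m = 50) and 61.5% (m = 150) at CV 0.4, 20.2% and 33.9% at CV 0.6, and 10.8% and 17.5% at CV 1.0.

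**The case against.** The mismatch may be only loose wording. F2 and both benefit statements in Section I speak of exposure, which MAC hours do measure, so changing one word in objective 4 would align the document. That is fair. It would remove the mismatch but leave an unadjusted historical comparison open to case mix.

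No bias has been shown. The retrospective group comes from the same hospital, and the study restricts age, ASA class and procedure and excludes emergencies and incarcerated hernias. The sample size, CV and duration gap used above are all assumed. This stands as a limit on the figures: they show what could happen, not what will. The plan, however, does not say that the retrospective group met the same restrictions, and it has no means of handling a difference if there is one.

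Time-weighted mean MAC has weaknesses of its own. F2 sets a pre-incision range of 0.8 to 1 MAC, while the background section's definition of failure in the quality-improvement review refers to more than 1 MAC. That figure is part of a failure definition, not a group mean, but a lower concentration could follow from the protocol's titration rather than from ultrasound. Induction may also be inhalational or intravenous, and it weighs more in a short case. Both points stand. A common measurement window largely deals with the second; the first can only be declared as a limitation.

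This is also one of four objectives in a pilot, with no power claim attached. That limits the weight of the point but does not remove it, since G1 cites secondary analyses as a reason for enrolling 150 rather than 99.

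**Conclusion.** The concern holds. As written, the plan cannot tell a lower concentration from shorter operations or a different case mix, so it does not answer objective 4. Under the stated assumptions, a 10% shortfall in case length at equal MAC raises the chance of a false reduction from 2.5% to between 9.5% and 59.5%, depending mainly on the CV. A 5% shortfall raises it to between 5.0% and 18.8%. Operations 5% longer would cut the chance of seeing a true 10% fall in concentration from 18.9%–59.5% to 8.3%–21.9% at CV 0.4 to 0.6, and from 9.5%–14.0% to 5.3%–6.9% at CV 1.0. The existence and direction of any such difference are unknown, and the unseen data sheet might record duration, although no analysis using it is planned. The point should be corrected before the comparison is run. The primary outcome, the block failure rate, is not affected.

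**What to change.** - For the concentration question, add time-weighted mean MAC: MAC hours divided by the hours over which they accrued, with the same start and end events in both groups. Compare it by regression adjusted for procedure type and age where both groups have them recorded.
- Keep MAC hours as F2's exposure measure, over the whole anesthetic so that time added by ultrasound checking or a repeat block is counted. Adjust for procedure type and age, and report durations by group. A duration-adjusted version should be a sensitivity analysis only.
- Describe the retrospective group: its size, dates, selection, procedures and durations.
- If hours cannot be recovered for that group, report both groups descriptively and draw no conclusion on objective 4.
- State that the comparison is exploratory, non-randomised and historical, and that it cannot separate ultrasound confirmation from the protocol's pre-incision titration or from unmeasured differences.

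The cost is analysis wording plus a check of the retrospective records for the MAC-hours window, duration, procedure type and age. The price is a weaker, exploratory claim on objective 4. No clinical care changes.

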Caudal blocks are one of the most commonly performed regional anesthetics in children and are performed daily for a host of infra-umbilical surgical procedures. A caudal block is an epidural injection, most commonly of local anesthetic into the epidural space as accessed via the sacral hiatus. In children, the sacral hiatus is a normally occurring aperture in which the epidural space may be accessed with extremely minimal risk; as neural tissue ends more proximally. Due to this measure of safety, caudal blocks are preferred in children when compared with standard lumbar epidurals. Caudal blocks are performed blindly using palpation and tactile feedback to assess if the medication is being administered in the correct location. As a result of blind injection, administration of local anesthetic totally or partially outside of the correct site can often be unnoticed or identified after a significant volume has already been injected. With the potential for toxicity of local anesthetic, this may result in either the inability to give a complete dose or an unintentional and often unnoticed sham block (incorrect site of injection).

Use of ultrasound has been proposed for identification of caudal block placement and correct medication spread. However, a recent review of the Pediatric Regional Anesthesia Network database reveals that ultrasound is reportedly only used in less than 3% of blocks. The benefit of ultrasound is safe and real-time confirmation of injection. Ultrasound allows the provider to determine with minimal local anesthetic or even saline injection if the correct space is accessed. Without ultrasound, failed blocks are either identified after significant percentage of the total dose of local anesthetic is incorrectly administered or intra or post operatively when the patient demonstrates a significant opioid requirement. This is problematic given that one of the primary benefits of a caudal block in children is the ability to avoid opioids.

Review of local practice here at Texas Children's Hospital for quality improvement purposes revealed a failure rate of caudal blocks to be 18%. Failure was defined as a heart rate increase with incision of >20% despite a caudal block and >1MAC of gas for the patient age. These patients all required opioids both intra and post operatively in addition to surgical levels of inhaled anesthetic agent.

Section D: Purpose and Objectives

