Patient: For the individual patient enrolled, there will be no deviation from the standard of practice of either the anesthetic or regional block. As nearly all providers perform this technique blindly, the patient will have the benefit of immediate recognition of incorrect block eliminating the possibility for inadvertent sham block. In addition, reduced block failure will result in less exposure to opioids and inhaled anesthetic agents.

Describe potential benefit(s) to society of the planned work.

The benefit from this study, should it show that ultrasound is superior for recognizing incorrect placement when compared with blind technique is that fewer inadvertent sham blocks may be performed. Additionally, if reduction of block failure by use of ultrasound can be established, reduced exposure to inhaled anesthetics which have potential adverse effects on neurodevelopment may be possible

Do anticipated benefits outweigh potential risks? Discuss the risk-to-benefit ratio.

The study benefits the participant that would undergo a caudal block using a blind technique in that immediate recognition of sham block would be possible allowing for correction of placement. The study would reduce the risk for patients undergoing caudal blocks with incorrect placement that provide a risk of the block with no benefit. This allows the patient to either benefit from the block or avoid wrongly placed medication should the block be aborted. As with all studies, there is a small risk of loss of confidentiality or data breach.

Section J: Consent Procedures

J1. Waiver of Consent

Will any portion of this research require a waiver of consent and authorization?

NA

J1a. Waiver of requirement for written documentation of Consent

Will this research require a waiver of the requirement for written documentation of informed consent?

NA

J2. Consent Procedures

Who will recruit subjects for this study?

PI
PI's staff

Describe how research population will be identified, recruitment procedures, any waiting period between informing the prospective participant and obtaining consent, steps taken to minimize the possibility of coercion or undue influence and consent procedures in detail.

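### The objective 4 MAC-hours comparison describes its trial side as ultrasound-confirmed blocks and has no rule for aborted or never-confirmed blocks, with no matching condition on the retrospective group

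*Combined protocol and SAP*

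**What the plan says.** Objective 4 (Section D) asks whether less inhaled agent can be used once ultrasound has shown where the block lies. F2 answers it by comparing MAC hours "in patients having undergone caudal block with ultrasound confirmation to those in the retrospective group gathered for quality improvement". The trial side is described by ultrasound confirmation. No corresponding condition is placed on the retrospective side.

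The background section, before Section D, describes one local quality-improvement review, which "revealed a failure rate of caudal blocks to be 18" percent. Its definition was clinical: "Failure was defined as a heart rate increase with incision of >20% despite a caudal block and >1MAC of gas for the patient age". On exposure it adds: "These patients all required opioids both intra and post operatively in addition to surgical levels of inhaled anesthetic agent".

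In the trial, a misplaced block is repeated. F2 says "If the provider feels they are not in the caudal space, they will re-do the procedure", and also "If the provider fails to identify incorrect location and this is noted by ultrasound, the SC will inform the provider to re-do the procedure". F2 then describes only what happens after a confirmed injection. The risk-benefit text in Section I allows for another outcome, in which the child may "either benefit from the block or avoid wrongly placed medication should the block be aborted". Objective 2 sets out to measure how often ultrasound can convert a misplaced block into a correct one, so complete correction is not assumed.

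G2 offers a t-test or Mann-Whitney test for continuous variables and names no analysis population. G1 allows 10% dropout, with an unrecognized sacral dimple given as an example of an open list.

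**The concern.** Whether a block is confirmed depends partly on how the attempt went, and it is known only after the child is enrolled. If the trial side is restricted to confirmed blocks, a child whose block was abandoned, or never seen in the right place, drops out. That child has no working caudal and would plausibly need more inhaled agent. The counterpart in past practice is a child whose misplacement went unnoticed, and nothing stated removes that child from the retrospective group. The two sides would then follow different rules, and the difference would favor ultrasound. Adjusting for case length or case mix would not bring the missing children back.

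The question for practice is whether scanning every planned caudal lowers exposure. Section I links lower exposure to a possible neurodevelopmental benefit, so an inflated reduction could carry weight with readers.

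**Working it through.** **The plan's own figure.** The only relevant number is the 18% failure rate. It comes without a numerator or denominator and cannot be reproduced, so it is taken as given. The plan states no MAC-hours figure, expected reduction or power for objective 4.

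**Inputs**
- f = 0.18, the failed share of the retrospective group (background section). That this review is the F2 comparator, with its failures included, is a fair inference but is not stated.
- k, the MAC hours of a failed or aborted block relative to a working block. The documents do not give it; assumed 1.25 to 1.5.
- u, the share of trial children whose block is aborted or never confirmed and who are dropped. The documents do not give it; assumed 0 to 10%. Of 150 children, 5% to 10% is 7.5 to 15.
- A working block is set to 1. For the first pass, every confirmed block is treated as working.

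**Formulas**
- Retrospective mean: m = 0.82 + 0.18k.
- Apparent reduction, confirmed blocks only: 1 − 1/m.
- Reduction with all attempted blocks kept: 1 − (1 + u(k − 1))/m.
- Bias, the difference between these two: u(k − 1)/m.

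**Results**
- k = 1.25: m = 0.82 + 0.225 = 1.045. The confirmed-only reduction is 1 − 1/1.045 = 4.3%.
- k = 1.5: m = 0.82 + 0.27 = 1.09. The confirmed-only reduction is 1 − 1/1.09 = 8.3%.

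| k | u | All attempted blocks kept | Confirmed only | Bias (points) |
|---|---|---|---|---|
| 1.25 | 0 | 4.3% | 4.3% | 0 |
| 1.25 | 5% | 3.1% | 4.3% | 0.0125/1.045 = 1.2 |
| 1.25 | 10% | 1.9% | 4.3% | 0.025/1.045 = 2.4 |
| 1.5 | 0 | 8.3% | 8.3% | 0 |
| 1.5 | 5% | 6.0% | 8.3% | 0.025/1.09 = 2.3 |
| 1.5 | 10% | 3.7% | 8.3% | 0.05/1.09 = 4.6 |

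The bias is the last column only. The 4.3% or 8.3% total is not bias: at u = 0 it is, in this model, the effect objective 4 looks for.

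**Share of the apparent reduction due to selection.** The bias divided by the confirmed-only reduction is u/0.18 whatever k is: 0.05/0.18 = 28% and 0.10/0.18 = 56%.

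**Allowing for clinical failures among confirmed blocks.** If a share c of confirmed children fail clinically, the bias becomes u(1 − c)(k − 1)/m and the apparent reduction (0.18 − c)(k − 1)/m. At u = c = 5% and k = 1.5, these are 0.02375/1.09 = 2.2 points out of 0.065/1.09 = 6.0%. The selection share is 0.0475/0.13 = 37%. The bias in points falls slightly, but it is a larger part of a smaller reduction.

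**The case against.** A reader might infer that failures are removed from the trial side only, and that the comparison would therefore favor ultrasound whether or not it helps. The documents do not support this. F2 has misplaced blocks re-done, whether the provider or the ultrasound operator detects them, and those children stay in. That is the intervention working, not selection. Failure in the retrospective review is a heart-rate response, while the trial condition is needle location. A confirmed child whose heart rate rises is not excluded, and objective 3 studies that response in confirmed children.

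Four further objections deserve weight.
- The F2 phrase may simply name the study cohort rather than act as a filter. That is possible, but no sentence in F2 or G2 settles it, and the literal reading excludes unconfirmed children.
- Section I mentions an aborted block only conditionally, and F2 describes only a re-do. The abort share may be zero, and then so is the bias. It cannot be known beforehand, which is a reason to fix the rule now.
- The retrospective review defined failure among children who had a caudal block, so abandoned attempts may be missing there too. Adding them to the trial side alone could then create an imbalance in the other direction. This objection stands, and the fix has to deal with it.
- There are more direct threats to this comparison. The trial targets 0.8 to 1 MAC before incision, the retrospective failures were defined above 1 MAC, and no adjustment for historical differences is planned. This is true, and the present point does not resolve it.

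**Conclusion.** The concern holds in a narrow form. F2 describes the trial side by a post-enrollment result, places no such condition on the retrospective side, and gives no rule for aborted or never-confirmed blocks. For assumed ratios of 1.25 to 1.5, losing 5% to 10% of trial children would overstate the reduction in MAC hours by about 1.2 to 4.6 percentage points; with no such losses there is no bias. The estimate also assumes that the retrospective group is the 18% review with its failures kept and abandoned attempts not filtered out. Severity is minor: this is a secondary objective of a self-described pilot, and the effect may be small.

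**What to change.** In F2 and G2, define the MAC-hours comparison set as all enrolled children in whom a caudal was attempted under the study procedure, whether or not ultrasound finally confirmed it. Children whose block was aborted contribute their recorded MAC hours. Only children found ineligible before any needle attempt, such as those with a previously unknown sacral dimple, leave the set. Report the confirmed-only comparison as secondary, and give the number aborted or never confirmed.

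Also state whether the retrospective group includes caudals that were attempted and abandoned. If it does not, say so and describe how the two sides will be put on the same rule, so that the change does not create the opposite imbalance.

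The cost is a sentence or two, plus recording MAC hours for unconfirmed children as for the others. It needs no extra patients and no change in care. The reported reduction may be less favorable. The other differences from the historical group remain and need their own treatment.

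### G1's only power statement assumes a 20% gain in success that its cited 92.9% baseline cannot yield and omits the inputs behind 99 patients; G2 gives the primary outcome, a single proportion, an odds ratio with no named comparator

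*Combined protocol and SAP*

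**What the plan says.** G1 cites an earlier study that "demonstrated an incidence of 7.1% subcutaneous bulging (failed block) when ultrasound was not used". It names the outcome in the words "Using our primary outcome of determination of block failure rate when performing blind (without ultrasound", and sets the effect by "assuming a difference of 20% increase in success rate would alter practice and thus be clinically significant using a one sample mean". With alpha 0.05 and 80% power it states that this "would require an enrollment of 99 patients, each serving as their own control". Enrolment is then raised to 150 for 10% dropout and for secondary analyses whose needs are not quantified.

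The G2 form asks "Which is the PRIMARY comparison/analysis". The only sentence in the answer that mentions the primary outcome is "Odds ratios will be noted for the primary outcome with confidence intervals displayed to achieve CI of 95" per cent. G2 also says in general terms that data will be presented as numbers and percentages where appropriate.

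Objective 1 in Section D is "Identify the rate at which blindly placed caudal blocks are not within the epidural space". F2 has the blinded provider judge the placement: "If the provider feels they are not in the caudal space, they will re-do the procedure". If the provider misses an error that ultrasound shows, the study collaborator asks for a repeat. The patient goes on to surgical preparation once ultrasound has confirmed the injection.

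**The concern.** G1 contains the only power statement in the plan. The effect it assumes does not fit the baseline beside it, and the test it names does not fit a yes/no outcome. A reader therefore cannot tell which hypothesis, effect or test the 80% refers to.

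The analysis in G2 adds to the difficulty. An odds ratio needs two things to compare, and the primary outcome is one rate. If the primary estimate is not defined before data are seen, both its numerator (all misplacements, or only those the provider missed) and its comparator can be chosen afterwards.

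**Working it through.** **Inputs.** From G1: blind failure 7.1%; a 20% increase in success, scale not stated; alpha 0.05, sidedness not stated; power 80%; 99 patients; 10% dropout; 150 enrolled. From the background section: a local failure rate of 18%, defined by heart-rate rise at incision rather than by needle position, and not used in G1.

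**1. Is the effect possible?** Baseline success is 1 − 0.071 = 0.929.
- Absolute: 0.929 + 0.20 = 1.129.
- Relative: 0.929 × 1.2 = 1.115.
- Largest possible gain: 1 − 0.929 = 0.071.

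From the 18% rate, success is 0.82. Absolute: 0.82 + 0.20 = 1.02. Relative: 0.82 × 1.2 = 0.984, the only reading that stays below 100%.

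**2. Can 99 be reproduced?** For a one-sample mean, two-sided, n = (1.960 + 0.8416)² × SD² / δ² = 7.849 × SD² / δ². With δ = 0.20 this is 196.2 × SD². G1 gives no SD, so those below are assumptions (noncentral-t result in brackets):
- Binomial SD at 7.1%: SD² = 0.071 × 0.929 = 0.0660, n = 12.9, so 13 (15).
- Maximum for one yes/no outcome: SD² = 0.25, n = 49.1, so 50 (52).
- Within-patient change from 20% failure to 0%: SD² = 0.20 × 0.80 = 0.16, n = 31.4, so 32 (34).

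The relative reading on the 18% rate, as a one-sample proportion, gives [(1.960 × √(0.82 × 0.18) + 0.8416 × √(0.984 × 0.016)) / 0.164]² = 27.4, so 28.

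Some sets of unstated inputs do come close to 99:
- δ = 0.20 with SD² = 0.5 gives 98.1, so 99 (101).
- A standardized effect of 0.25, one-sided, gives 98.9, so 99 (101).
- 18% against 7.1% (10.9 points) with SD 0.384 gives 97.5, so 98 (100).

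The documents do not say which of these, if any, was used, and the last does not use the 20%.

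**3. From 99 to 150.** 99 / 0.90 = 110, so 150 − 110 = 40 patients rest on the unquantified secondary analyses.

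**4. What would the odds ratio compare?** If it is blind against ultrasound-confirmed placement within patient, the matched odds ratio is the number wrong then right divided by the number right then wrong. F2 repeats the block until ultrasound confirms it, so the denominator should be zero. With 10 blind misplacements the ratio would be 10/0.

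**5. What 150 patients deliver for objective 1.** Evaluable, applying G1's 10%: 150 × 0.90 = 135. Exact (Clopper–Pearson) 95% limits for x of n are the 0.025 quantile of Beta(x, n − x + 1) and the 0.975 quantile of Beta(x + 1, n − x):

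| Misplaced of 135 | Rate | Exact 95% CI |
|---|---|---|
| 10 | 7.4% | 3.6% to 13.2% |
| 17 | 12.6% | 7.5% to 19.4% |
| 18 | 13.3% | 8.1% to 20.3% |
| 24 | 17.8% | 11.7% to 25.3% |
| 36 | 26.7% | 19.4% to 35.0% |
| 37 | 27.4% | 20.1% to 35.7% |

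A rate of 20% is excluded from above at 17 or fewer and from below at 37 or more.

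**The case against.** The best defence of G1 is that 20% is a practice-change threshold and 7.1% only background. G1 never says that 92.9% is the null or the expected rate in this trial. If the threshold means a blind failure rate of at least 20%, nothing exceeds 100%. That reading is coherent, but G1 does not state it: it speaks of an increase in success directly after citing a success rate that leaves 7.1 points of room. The sponsor may also hold inputs that were not printed. Printing them could make 99 derivable, but would not make a 20% gain possible from 92.9%.

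On G2, a reader might infer that the failure rate will not be reported at all. The text does not support that: the general sentence on numbers and percentages covers it. What is missing is a confidence interval for that proportion and a comparator for the odds ratio.

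A reader might also infer that no odds ratio could be estimated. That goes too far. The zero cell applies to blind against ultrasound-confirmed placement. F2 also yields the provider's judgement alongside the ultrasound finding, where disagreement can run both ways, and Section I presents recognition of misplacement as the hoped-for advantage of ultrasound. Predictors of failure are another possibility. G2 names none of these, so the gap stands.

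On the numerator, objective 1 points to all misplacements, but the background and Section I stress unnoticed ones. F2 refers to a data sheet that is not in the available text and may separate the two. The choice is the sponsor's to confirm. Finally, F1 classes the study as a pilot. That lowers the stakes, but G1 still chose to make a power claim.

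**Conclusion.** The point holds as a defect in the justification and in the definition of the primary analysis. On the one baseline G1 cites, the assumed gain is impossible on either scale (112.9% or 111.5%, against a ceiling of 7.1 points). The figure of 99 is underivable, because SD, null value, sidedness and scale are absent and a mean is named for a yes/no outcome. The primary outcome is one proportion, yet the only method tied to it is an odds ratio without a comparator.

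Two stronger readings are tempting and should not be drawn. One is that 99 is a miscalculation: several sets of unstated inputs give 99 or close to it, so the figure cannot be shown wrong. The other is that 150 patients are too few: with 135 evaluable, a rate near 7% is estimated with an interval of 3.6% to 13.2%, which is useful for objective 1. The precision figures assume that G1's 10% dropout applies to the 150 enrolled and that each evaluable patient contributes one first blind placement.

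This should be fixed before data are seen.

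**What to change.** **G1.** Keep 150. Replace the assumed gain in success, the one-sample-mean test and the claim of 99 patients at 80% power with:

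> With about 135 evaluable patients (150 less 10%), the exact 95% CI for the blind misplacement rate is 3.6% to 13.2% if 10 are misplaced and 11.7% to 25.3% if 24 are misplaced.

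If a practice-change threshold is kept, state it as a blind misplacement rate and compare it with this interval. For example, a 20% rate is excluded at 17 or fewer of 135.

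**G2.** State:

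> Primary analysis: the proportion of first blind placements that ultrasound shows outside the caudal/epidural space, with exact 95% CI.

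Count all such misplacements, following objective 1, and report separately those the provider did not recognise. The sponsor should confirm this choice before data are seen. Keep an odds ratio only as a secondary analysis with a named comparator, such as provider judgement versus ultrasound or a named predictor of failure.

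**Cost.** Wording only. Enrolment and procedures do not change; the sponsor gives up a power claim that the text does not support.
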